5 STUDY OBJECTIVES

It is the objective of the planned study to investigate the efficacy and safety of two different volume replacement regimen with gelatine solutions.

5.1 Primary Objective and Primary Variable(s)

5.1.1 Primary Objective

The primary objective of the study is to assess the intra-operative change of the base excess and chloride after treatment of a balanced volume replacement regimen (balanced gelofusine solution combined with a balanced electrolyte solution) compared with a non-balanced volume replacement regimen (non-balanced gelatine solution combined with a non-balanced electrolyte solution) in adult patients undergoing elective abdominal surgery.

5.1.2 Primary Variable

[figure not shown]
The primary variable of the study is the difference in the change of the base excess and chloride (baseline – immediately after end of surgery) after treatment between the two volume replacement regimen in adult patients undergoing abdominal surgery. (see section 10 for further details)

5.2 Secondary Objectives and Secondary Variables

Secondary objectives are safety and efficacy of the two different volume replacement regimen expressed by parameters such as arterial blood gas analysis, coagulation status, renal function, requirements of blood products, adverse events, hemodynamics, IP administration, clinical outcome, demographic data and surgery related data. (see section 10 for further details)

6 STUDY DESIGN

This is a prospective, controlled, randomized, double-blind, bicentre phase III study performed in 2 parallel groups. Comparison will be made of an Investigational Test Product (i.e. Gelofusine® Balanced) combined with a standard balanced electrolyte solution (i.e. Sterofundin® ISO) with an Investigational Reference Product (i.e. Gelafundin 4%) combined with a standard non-balanced electrolyte solution (i.e. NaCl 0.9%). In total 64 adult male and female patients will be included in the study. The aim is to study half of the patients in Aachen and the other half in Frankfurt/Main with half of the patients treated with the balanced regimen and the other half with the unbalanced regimen, each.

7 SELECTION AND WITHDRAWAL OF PATIENTS

7.1 Informed Consent

An informed consent, written in accordance with the origins of the Declaration of Helsinki (Appendix 1) and the applicable laws of the country has to be obtained from all patients.

The patient will sign the Informed Consent Form before s/he enters the study, i.e. before screening bloods, screening assessments or any other study-related activity. The Investigator will explain the nature, purpose and risks of the study and provide the patient with a copy of the patient information. The patient will be given sufficient time (preferably one day in advance) to consider the study's implications before deciding whether to participate.

Should there be any amendments to the Final Protocol, such that would directly affect the patient's participation in the study e.g. a change in any procedure, the Informed Consent Form must be amended to incorporate this modification and the patient's informed re-consent must be obtained.

7.2 Patient Inclusion Criteria

The following inclusion criteria apply:

- Male or female patients ≥ 18 years of age and ≤ 90 years of age.
Women of child bearing potential must test negative on standard pregnancy test (urine dipsticks).
- Patients scheduled to undergo elective abdominal surgery (e.g. rectal resection, liver resection, open bowel resection, duodenopancreatectomy)
- Scheduled intraoperative volume requirement of at least 15 mL/kg body weight (Broca) gelatine solution.
- Patients who are willing to give voluntary consent to participate in the study, following a full explanation of the nature and purpose of the study, by signing the informed consent form approved by the Institutional Ethics Committee (IEC) prior to all evaluations.

7.3 Patient Exclusion Criteria

Patients will not be considered for participation in the study if any of the following criteria listed below apply:

- Patients of ASA-class $> III$
- Patients suffering from known hypersensitivity to gelatine or to any of the constituents of the gelofusine solutions
- Patients treated with other colloid solutions and / or blood products 24 hours prior to surgery
- Patients on hemodialysis
- Patients suffering from decompensated renal function (i.e. serum creatinine > 3.0 mg/dL)
- Patients suffering from

- Hypervolemia
 - Hyperhydration
 - Severe blood coagulation disorders
 - Hyponatremia (serum(Na⁺) < 130 mmol/L)
 - Hyperchloremia (serum(Cl⁻) > 110 mmol/L)
 - Hypercalcaemia (serum(Ca⁺⁺ - total) > 3 mmol/L or serum (Ca⁺⁺-free) > 1.5 mmol/L)
 - Metabolic alkalosis
 - Severe heart insufficiency
 - Severe generalized edema
 - Intracranial haemorrhage
 - Hyperkalaemia (serum(K⁺) > 5.5 mmol/L)
 - Estimated perioperative need for blood products of more than 3.5 mL/kg body weight (Broca)
 - Lactation period
 - Simultaneous participation in another clinical trial
 - Emergencies
 - Patients suffering from
 - moderate heart or lung insufficiency
 - moderate lung edema
 - hypertonia
 - eclampsia
- who do not allow the IP regimen as required.

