	
 ○ Severe blood coagulation disorders ○ Hyponatremia (serum(Na⁺) > 150 mmol/L) ○ Hyperchloremia (serum(Cl⁻) > 110 mmol/L) ○ Hypercalcaemia (serum(Ca⁺⁺ - total) > 3 mmol/L or serum (Ca⁺⁺-free) > 1.5 mmol/L) ○ Metabolic alkalosis ○ Severe heart insufficiency ○ Severe generalized edema ○ Intracranial haemorrhage ○ Hyperkalaemia (serum(K⁺) > 5.5 mmol/L) ▪ Estimated perioperative need for blood products of more than 3.5 mL/kg body weight (Broca) ▪ Lactation period ▪ Simultaneous participation in another clinical trial ▪ Emergencies ▪ Patients suffering from 
 ○ moderate heart or lung insufficiency ○ moderate lung edema ○ hypertonia ○ eclampsia 
who do not allow the IP regimen as required.
																												

Investigational Test Product
	
The investigational test product (Gelifusine® Balanced) contains
 
Composition:
 
1000 mL solution contain
 
 
 Gelatine polysuccinate (= modified fluid gelatine)	40.00 g	
 
 Sodium chloride	5.55 g	
 
 Sodium acetate trihydrate	3.27 g	
 
 Potassium chloride	0.30 g	
 
 Calcium chloride dihydrate	0.15 g	
 
 Magnesium chloride hexahydrate	0.20 g	
 
 
Excipients for pH-adjustment:
 
 
 Sodium hydroxide 40%	0 – 0.133 g	
 
 Hydrochloric acid 20%	0 – 0.182 g	
 
 
Electrolyte concentrations
 
 
 Sodium	151 mmol/L	
 
 Chloride	103 mmol/L	
 
 Potassium	4 mmol/L	
 
 Calcium	1 mmol/L	
 
 Magnesium	1 mmol/L	
 
 Bicarbonate as Acetate	24 mmol/L	
 
 
Molecular weight, weight average : 30 000 Dalton
 
Molecular weight, number average : 23 200 Dalton
	Gelatine polysuccinate (= modified fluid gelatine)	40.00 g	Sodium chloride	5.55 g	Sodium acetate trihydrate	3.27 g	Potassium chloride	0.30 g	Calcium chloride dihydrate	0.15 g	Magnesium chloride hexahydrate	0.20 g	Sodium hydroxide 40%	0 – 0.133 g	Hydrochloric acid 20%	0 – 0.182 g	Sodium	151 mmol/L	Chloride	103 mmol/L	Potassium	4 mmol/L	Calcium	1 mmol/L	Magnesium	1 mmol/L	Bicarbonate as Acetate	24 mmol/L

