11.5 Pregnancies

Not applicable, because the study is performed in the operation room and the ICU / IMC.

12 STUDY SCHEDULE**12.1 Procedures at Each Visit**

Pre-operatively:

- Verification of inclusion and exclusion criteria, including informed consent
- Blood samples for laboratory evaluation of electrolyte and coagulation status
- Urine sample in women of child bearing potential for pregnancy testing
- Demographic data, history
- Apfel-Score
- Pre-operative medication / therapy as medically indicated and standardized (including pre-operative fasting time)

Pre-anesthesia:

- Randomization (i.e. supply of blinded study samples)
- Set of catheters (e.g. arterial / central venous catheter)
- Baseline laboratory and hemodynamics
- Blood sampling for baseline laboratory evaluation
- Baseline ROTEM and baseline platelet aggregation
- Administration of first bottle of investigational products, i.e. crystalloid component
- Drug monitoring and tolerance
- Induction of anesthesia
- Concomitant medication and therapy (including concomitant medication and therapy prior induction of anesthesia; including blood products acc. to trigger)
- Adverse events/ reactions

After induction of anesthesia/prior surgery :

- Administration of investigational products
- Time on ventilator
- Final positioning of patient in operating theatre
- Set of urinary catheter for urine sampling
- Hemodynamics
- Blood sampling for laboratory evaluation
- Drug monitoring and tolerance
- Concomitant medication and therapy (including concomitant medication and therapy prior induction of anesthesia; including blood products acc. to trigger)
- Adverse events / reactions

During surgery :

- Administration of investigational products for volume replacement
- Surgery related data
- Intraoperative hemodynamics (every 15 min; CVP minus PEEP and MAP serve as trigger for IP-administration)
- Blood sampling for laboratory evaluation (blood gas analysis every 15 minutes, recovery room hourly)
- Drug monitoring and tolerance
- Recording of blood loss (drainage blood loss and estimated blood loss)
- if applicable, blood product administration
- Time on ventilation
- Concomitant medication and therapy
- Adverse events / reactions

End of surgery:

- Administration of investigational products for volume replacement according to algorithm
- Surgery related data
- Hemodynamics
- Blood sampling for laboratory evaluation
- Drug monitoring and tolerance

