Because the product does not substitute lost plasma protein, it is advisable to check the plasma protein concentrations.

Gelatine solutions must not be infused through the same infusion line together with blood or blood products (packed cells, plasma and plasma fractions).

Laboratory blood tests (blood group or irregular antigens) are possible after gelatine infusions. Nevertheless it is recommended to draw blood samples before the infusion of gelatin solutions in order to avoid hampered interpretation of results.

Gelatine solutions may have an influence on the following clinical-chemical tests, leading to falsely high values:

- erythrocyte sedimentation rate,
- specific gravity of urine,
- unspecific protein assays, e.g. the biuret method.

Sterofundin ISO:

High volume infusion must only be used under specific monitoring in patients with mild to moderate cardiac or pulmonary failure.

Solutions containing sodium chloride should be administered with caution to patients with

- mild to moderate cardiac insufficiency, peripheral or pulmonary oedema or extracellular hyperhydration
- hypernatremia, hyperchloremia, hypertonic dehydration, hypertension, impaired renal function, present or imminent eclampsia, aldosteronism or other conditions or treatment (e.g. corticoids/steroids) associated with sodium retention

Solutions containing potassium salts should be administered with caution to patients with cardiac disease, conditions predisposing to hyperkalemia such as renal or adrenocortical insufficiency, acute dehydration, or extensive tissue destruction as occurs with severe burns.

Because of the presence of calcium

- Care should be taken to prevent extravasation during intravenous infusion.
- The solution should be given cautiously to patients with impaired renal function or diseases associated with elevated vitamin D concentrations such as sarcoidosis.

In case of concomitant blood transfusion, the solution must not be administered via the same infusion set.

Solutions containing metabolisable anions should be administered cautiously to patients with respiratory impairment. Monitoring of the serum electrolytes, fluid balance, and pH is necessary.

During long-term parenteral treatment, a convenient nutritive supply must be given to the patient.

Sodium Chloride 0.9%:

Sodium Chloride 0.9% should only be administered with caution in cases of

- hypokalemia
- hypernatremia
- hyperchloremia

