- disorders where restriction of sodium intake is indicated, such as cardiac insufficiency, generalized oedema, pulmonary oedema, hypertension, eclampsia, severe renal insufficiency.

Clinical monitoring should include checks of the serum ionogram, the water balance, and the acid-base status.

High infusion rates should be avoided in cases of hypertonic dehydration because of possible increases of plasma osmolarity and plasma sodium concentration.

Each patient will be checked if he/she can be treated according to the protocol or not. Patients at risk should be treated with caution and be excluded if the IP regimen can not be applied as required.

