14.8 Patient selection for analyses

An Intent-To-Treat (ITT) analysis and Full Analysis Set (FAS) respectively is planned as primary.

Additionally, an Per-Protocol (PP) or Valid Case Analysis Set (VCAS) respectively will be performed i. e. all patients where none of the following events occurred:

- Stop of treatment due to adverse reaction
- severe violation of study protocol

The results of both analyses will be compared and possible differences have to be discussed accordingly.

The definitions for any population groups chosen for analysis (e.g. all patients randomized, intent-to-treat, per-protocol, completers) will be provided in the SAP. Decision on analysis of the respective study population will be performed prior unblinding.

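### The sodium exclusion limit is above 150 mmol/L in the synopsis and below 130 mmol/L in section 7.3, under the same label

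*Protocol*

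**What the plan says.** The protocol lists its exclusion criteria twice, in the synopsis (section 3) and in section 7.3.

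- Synopsis: "Hyponatremia (serum(Na⁺) > 150 mmol/L").
- Section 7.3: "Hyponatremia (serum(Na⁺) < 130 mmol/L").

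The neighbouring entries in section 7.3, for example "Hyperchloremia (serum(Cl⁻) > 110 mmol/L") and "Hyperkalaemia (serum(K⁺) > 5.5 mmol/L"), are the same in the synopsis.

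Three other places bear on the point:

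- Section 12.1 schedules the following before surgery: "Blood samples for laboratory evaluation of electrolyte and coagulation status".
- Section 12.4 advises caution with sodium-chloride-containing solutions in several conditions, among them "hypernatremia, hyperchloremia, hypertonic dehydration, hypertension, impaired renal function". It closes with a general rule: "Patients at risk should be treated with caution and be excluded if the IP regimen can not be applied as required".
- Section 14.8 removes from the per-protocol set any patient with a "severe violation of study protocol".

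**The concern.** An eligibility limit has to give the same answer wherever a site looks it up. Here the two lists disagree on sign and figure, and the synopsis entry puts a high-sodium limit under a low-sodium label. Correcting the label in the synopsis to hypernatremia would not reconcile them: the synopsis would then exclude high sodium and section 7.3 low sodium.

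The main stake is eligibility and safety screening. If section 7.3 governs, no numeric limit keeps a hypernatremic patient out, although all four study fluids contain 140 to 154 mmol/L sodium (section 8.1.1) and section 12.4 names hypernatremia among the cautions. If the synopsis figure governs, no numeric limit keeps a hyponatremic patient out. A secondary point is that a sodium-related eligibility violation cannot be judged consistently while the limit itself is in doubt.

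**Working it through.** The protocol gives no figure to reproduce here, so the check is a comparison of the numeric electrolyte limits in the two lists.

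| Criterion | Synopsis (section 3) | Section 7.3 | Same? |
|---|---|---|---|
| Chloride, mmol/L | > 110 | > 110 | yes |
| Calcium, total, mmol/L | > 3 | > 3 | yes |
| Calcium, free, mmol/L | > 1.5 | > 1.5 | yes |
| Potassium, mmol/L | > 5.5 | > 5.5 | yes |
| Sodium, mmol/L | > 150 | < 130 | **no: sign and figure differ** |

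Four of the five limits agree. The creatinine limit (> 3.0 mg/dL) and the limit on expected blood products (> 3.5 mL/kg) also agree.

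**What each sodium limit does.** No value is both above 150 and below 130, so {Na⁺ > 150} and {Na⁺ < 130} do not intersect.

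| Sodium, mmol/L | Synopsis figure | Section 7.3 figure |
|---|---|---|
| 127 | not excluded (the label still points to exclusion) | excluded |
| 130 to 150 | not excluded | not excluded |
| 152 | excluded | not excluded |

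**Can the intent be inferred?** The evidence points both ways.

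- *For the low limit:* both lists use the word hyponatremia, and the entry in section 7.3 is coherent in word, sign and figure.
- *For the high limit:* every other numeric electrolyte exclusion is for a value that is too high. Hypernatremia appears in the section 12.4 precautions for the gelatine solutions, Sterofundin ISO and NaCl 0.9%, and section 11.4 names it as a possible result of larger amounts of NaCl 0.9%.

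No other section states a sodium limit for entry or says which list prevails.

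**The case against.** The strongest reply is that section 7.3 is the full eligibility section, is coherent, and is what a site would follow. On that view the synopsis entry is a slip, or even a misreading of the PDF text, since product names nearby in the synopsis are also misspelt. Both lists name hyponatremia, so a patient at 127 mmol/L would be excluded under either, and only values above 150 remain in doubt. The precautions in section 12.4 treat hypernatremia as a reason for care and monitoring, not as a contraindication, so the protocol is not bound to set an upper limit. Each patient is also checked individually, and sodium is measured at baseline and every 15 minutes during surgery. Finally, the per-protocol link is weak: section 14.8 leaves the population definitions to the SAP, and nothing says that a sodium violation would count as severe.

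Much of this limits the weight of the point. The label does soften the conflict at the low end, an upper sodium limit is a clinical choice, and the per-protocol consequence is only a supporting point. The conflict itself remains. One misread word cannot explain a difference in both sign and figure, although a look at the printed page is worthwhile. That sites would probably follow section 7.3 does not show that its figure is the intended one. The case-by-case check in section 12.4 and the intraoperative measurements set no sodium limit for entry.

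**Conclusion.** The protocol contradicts itself on an eligibility threshold that sites apply at screening, and it should be corrected. The two sodium limits agree only from 130 to 150 mmol/L. The clearest practical conflict is above 150 mmol/L, where one list excludes the patient and the other does not.

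The reach is limited. The protocol gives no screening data, so the number affected is unknown; that it is small is a judgement based on elective patients of ASA class III or below. The primary intention-to-treat (full analysis set) comparison, the type I error, the power and the sample size do not depend on the sodium limit.

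The conclusion assumes that both entries are printed as they read here. Which limit was intended cannot be settled from the protocol.

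**What to change.** The sponsor's clinical team should confirm whether the low limit, the high limit or both apply. If both are meant, the criterion could read: hyponatremia, Na⁺ < 130 mmol/L, or hypernatremia, Na⁺ > 150 mmol/L. The same term, sign and figure should then appear in the synopsis, section 7.3 and the CRF eligibility page.

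The cost is a one-line amendment under section 17.7 and a check of the CRF page.

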7.4 Stopping and Discontinuation Criteria

When the study in an individual patient is terminated, the nature of termination must be documented (scheduled end or premature termination/discontinuation). In the event of premature termination/discontinuation, justification has to be given and it is to be recorded who took the decision to discontinue.

If the study as a whole is prematurely terminated or suspended, the concerned IEC and the regulatory authorities will be informed promptly and provided with the reasons for the termination or suspension by the sponsor.

7.4.1 Discontinuation Criteria Related to the Study

Criteria for discontinuation / termination of the entire clinical study include (not exclusively)

- Unexpected high frequency of serious adverse events/reactions during the study which does not justify a continuation of the study. (cf. Frequency as outlined in the SmPCs). Especially renal insufficiency, severe bleeding and anaphylactic reactions should be monitored. In case any of these events occurs in more than 10% of the scheduled 64 patients (i.e. 7 patients) the study is to be discontinued.

- Occurrence of suspected unexpected serious adverse reaction(s) which does/do not justify a continuation of the study.
- Patients cannot be recruited in sufficient numbers. Not sufficient is defined as recruitment of less than 2 patients per month on average.

7.4.2 Discontinuation Criteria Related to the Study Site

Discontinuation of the clinical study in an individual study site may occur because of various reasons including but not limited to

- Failure of Investigator to comply with the ICH-GCP and/or applicable regulatory requirements.
- Submission of knowingly false or incomplete information from the site to B. Braun Melsungen AG, Study Monitor, or the authorities.
- Repeated non-adherence to protocol requirements including insufficient data quality (missing data in CRFs occurring repeatedly).
- Failure of the Investigator at a site to enrol patients into the study at an acceptable rate, i.e. less than 12 patients per 6 months.
- Personnel change without appropriate information to the sponsor.

7.4.3 Discontinuation Criteria related to the Patient

The patients will be advised in the Informed Consent Forms that they have the right to withdraw from the study at any time without prejudice, and may be withdrawn at the Investigator's / Sponsor's discretion at any time, when this is considered to be in the interest of the patient.

Withdrawal of individual patients from treatment or from the study respectively could be caused by the following reasons but not limited to

Withdrawn by the Investigator due to

- Adverse Event, Serious Adverse Event (including pregnancy)
- Protocol deviation (e.g. dosing regimen, failure to comply with protocol)
- Administration of an excluded medication
- Clinical significant abnormal laboratory value(s)

which leads to inacceptance of further remaining on treatment or in the study as considered by the investigator.

The patient requested withdrawal due to:

- An Adverse Event for which the Investigator did not consider removal from the treatment/study necessary
- Perceived insufficient therapeutic effect
- Perceived sufficient therapeutic effect
- Withdrawal of consent

In case a patient does not reappear to any scheduled visit (i. e. is lost to follow-up) reasonable effort should be made to contact this patient in order to complete

assessments and/or to evaluate reason for non-appearance (possibly implicit withdrawal of consent).

In the event that a patient withdraws consent or is withdrawn from the study, the study termination page in the CRF (including a final examination, if applicable) should be completed indicating that the study was prematurely terminated. The Investigator should record the date of the withdrawal, the person who initiated withdrawal and the reason for withdrawal.

7.5 Randomization, Blinding and Unblinding

Patients will be randomized to either treatment in a 1:1 ratio.

The list of treatment assignments considering the stratification for site will be generated by a statistician (not involved in the study data analyses) comprised of consecutive blocks with the order of assignments chosen at random (e.g.: random permuted block of size 4, 6 or 8). The randomization list will be prepared prior to the initiation of the study and will remain with the statistician. A signed copy of the randomization list will be sent to the independent pharmacy responsible for the blinding of the samples. Based on this randomization list the statistician will also issue sets of emergency envelopes for each participating site (i.e. the Principal Investigators) for emergency unblinding. The sponsor, i.e. qualified person study supply and drug safety officer will also receive a complete set of emergency envelopes for emergency situations.

Patients who are eligible for inclusion into the study shall receive an increasing sequential patient number in accordance with the order of their inclusion in the study and according to stratum. The random numbers will be issued including center stratum (1 = Aachen or 2 = Frankfurt/Main).

Blinding will be performed by an independent pharmacy providing blinded samples. The blinded samples will be sent to the investigators who will store and manage them.

For emergency unblinding the statistician will provide sealed envelopes with the patient number printed for both the coordinating investigator and the principal investigator which will be sent to the study centers prior start of the study. When breaking the seal of an envelope the respective treatment for the individual patient is stated. The code may only be broken when this is relevant for the safety of the patient. Any premature code break (e.g. unblinding due to a Serious Adverse Event, accidental unblinding) should promptly be documented and reported to the Sponsor including explanation/justification. Emergency unblinding may be discussed with the Sponsor prior breaking the seal if possible, i.e. if this is not affecting the patient's safety. Upon study completion all emergency envelopes will be retrieved by the study monitor.

After closure of the database and determination of the analysis populations (in a blinded data review meeting if appropriate) the study will be unblinded.

The population will only be stratified with regard to

- center

This stratification variable will be included as covariate in the primary analysis (according to CPMP/EWP/2863/99).

